#### 8.7.1.1.3 EXPLORATORY ENDPOINTS

- Duration of response (DOR) by IIR is defined as the time from the date a response was first documented until the date of the first documentation of PD or date of death from any case.
- Disease control rate (DCR) by IIR is the proportion of subjects who have a best overall response of CR or PR or stable disease (SD). In this context, stable disease is defined as stable disease at  $\geq 7$  weeks after randomization to be considered best overall response.
- Clinical benefit rate (CBR) by IIR is the proportion of subjects who have best overall response of CR or PR or durable SD (duration of SD  $\geq 23$  weeks after randomization).
- Proportion of subjects who achieve complete removal of baseline lesions following completion of chemotherapy.
- Blood and tumor biomarkers will be assessed for identifying potential correlation with clinical outcomes-related endpoints.
- All efficacy endpoints above (except OS) will be evaluated by both IIR and investigator assessment using RECIST 1.1.

#### 8.7.1.2 Definitions of Analysis Sets

The Full Analysis Set (Intent-to-Treat Analysis [ITT]) includes all randomized subjects regardless of the treatment actually received. This is the primary analysis population used for the efficacy analyses which will be based on the ITT principle.

The Per Protocol Analysis Set includes those subjects from the ITT set who received at least 1 dose of any study drug, had no major protocol deviations, and had both baseline and at least one postbaseline tumor assessment. Subjects for whom death occurred prior to the first postbaseline tumor assessment will also be included. The per protocol analysis set will be the secondary analysis set for efficacy endpoints.

The Safety Analysis Set includes subjects who received at least 1 dose of any study drug. This is the analysis population used for all safety analyses which will be based on as-treated principle.

Population Pharmacokinetic (PK) Analysis Set includes the subjects who have received at least 1 dose of lenvatinib with documented dosing history and have measurable plasma levels of lenvatinib.

The Pharmacodynamic Analysis Set includes subjects who received at least 1 dose of study drug and had sufficient pharmacodynamic data (eg, at least 1 evaluable/measurable pharmacodynamic parameter).

The HRQoL Analysis Set will consist of all randomized subjects who have received at least 1 dose of study medication, and have completed at least 1 patient-reported outcome (PRO) assessment beyond baseline. For PRO analysis, subjects will be analyzed as randomized and not according to treatment actually received.

### 8.7.1.3 Subject Disposition

Reasons for screening failure will be summarized.

The number and percentage of subjects who completed the study will be summarized by treatment group, and for overall, and the number and percentage of subjects who discontinued prematurely will also be summarized by reason for discontinuation.

### 8.7.1.4 Demographic and Other Baseline Characteristics

Demographic and other baseline characteristics for the Full Analysis Set will be summarized using descriptive statistics. Continuous demographic and baseline variables (including age, sex, race, height, and weight) will be summarized using n (number of subjects with available data), mean, standard deviation, median, quartiles 1 and 3, and range (minimum and maximum) unless otherwise specified. Categorical variables will be summarized by number and percentage.

### 8.7.1.5 Prior and Concomitant Therapy

All investigator terms for medications recorded in the CRF will be coded to an 11-digit code using the World Health Organization Drug Dictionary (WHO DD). Concomitant medications will be further coded to the appropriate Anatomical Therapeutic Chemical (ATC) class indicating therapeutic classification. Prior medications will be defined as medications that started prior to the first dose of study drug and were either continued during the study or stopped prior to the first dose of study drug. Concomitant medications will be defined as medications that (1) started before the first dose of study drug and were continuing at the time of the first dose of study drug, or (2) started on or after the date of the first dose of study drug up to 30 days after the subject's last dose. All medications will be summarized and listed by drug and drug class and by treatment arm.

### 8.7.1.6 Efficacy Analyses

Efficacy analyses will be based primarily on the Full Analysis Set.

All the statistical analysis will be conducted at the PFS-1y/OS-1y analysis data cutoff date (ie, when the last subject has completed 18 cycles of treatment or discontinues before the end of Cycle 18, whichever occurs first), including the analysis of PFS-4m rate. Additional follow-up analysis will be based on the date of data cutoff for the additional follow-up analysis for OS or at the time of last subject last visit, whichever occurs later.

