**Control Arm (Arm B): Ifosfamide + Etoposide**

Ifosfamide 3000 mg/m^2/day, IV, daily for 3 consecutive days (Day 1 to 3), every 21 days, for a maximum of 5 cycles.

Etoposide 100 mg/m^2/day, IV, daily for 3 consecutive days (Day 1 to 3), every 21 days, for a maximum of 5 cycles.

Before dose administration on Day 1 of each cycle and prior to a change in dose due to dose reduction, the amount of lenvatinib needed for each subject must be calculated as follows:

$$\text{Scheduled dose (mg/m}^2\text{)} \times \text{body surface area (BSA) (m}^2\text{)} = \text{lenvatinib dose (mg)}$$

Body surface area (BSA) will be calculated using the method that is accepted and customarily used by the clinical site. BSA must be calculated on Day 1 of each cycle based on the subject's current height and body weight. BSA will be used to determine the amount of lenvatinib for each subject. BSA should not be corrected for amputation. The dose should be rounded to the nearest whole number. After adjustment for BSA, the daily dose of lenvatinib should not exceed 24 mg daily.

Subjects will receive study treatment as continuous 21-day cycles in both treatment arms. Treatment cycles will be counted continuously regardless of dose interruptions. If chemotherapy administration is precluded on Day 1 of a treatment cycle, the subject may resume treatment once recovered at the discretion of investigator. Subsequent chemotherapy will be administered every 21 ( $\pm 1$ ) days starting from the timepoint it was resumed.

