### **During Post-treatment Follow-up**

Subjects who discontinue treatment without PD will have tumor assessments performed as per the appropriate tumor assessment schedule) or sooner if clinically indicated, for documented PD or until another anticancer therapy is initiated, whichever occurs first.

After data cutoff for PFS-1y and OS-1y analysis, tumor assessments may be performed as clinically indicated as per the institutional guidelines, following the prevailing local standard of care. All subjects will be followed for survival for 2 years after end of treatment or until death, unless the study is terminated by the sponsor, or the subject discontinues due to withdrawal of consent, or is lost to follow-up.

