**Table 5 Schedule of Assessments in Study E7080-G000-230 – Randomization Phase**

Phase	Prerandomization		Randomization a (All cycles are 21 days in duration)																		
	Screening b	Baseline c	Treatment d																Off-Tx	Follow-up e	
Period	1	2	3	4	5	6	7	8	9	10	11	12	13	14	15	16	17	18+			
Visit	1	2	3	4	5	6	7	8	9	10	11	12	13	14	15	16	17	18+			
Cycle			Cycle 1			Cycle 2			Cycle 3			Cycle 4			Cycle 5			Cycle 6-X			
Day	-28 to -2	-1	1	8	15	1	8	15	1	8	15	1	8	15	1	8	15	1			
Procedures/Assessments																					
Informed consent	X																				
Inclusion/exclusion	X	X																			
Randomization (IVRS)			X																		
Demographic data	X																				
Medical/surgical history	X	X																			
Prior medication/ procedures	X	X																			
Pregnancy test f	X	X				X			X			X			X			X	X	X	X
Lansky play score/ Karnofsky PS g	X	X	X			X			X			X			X			X		X	
TNM Staging	X																				
Physical examination h	X	X	X		X	X		X	X			X			X			X	X	X	X
Vital signs i	X	X	X	X j	X	X		X	X			X			X			X	X	X	X
12-lead ECG k	X		X			X												X	X		
Echocardiogram l	X	Performed every 16±2 weeks following the first dose of study drug or sooner, if clinically indicated																X			
Clinical chemistry and hematology m	X	X			X	X		X	X			X			X			X	X	X	X
Urine dipstick testing n	X	X			X	X		X	X			X			X			X	X	X	X
PK blood samples o			X		X	X															
Study treatment p			Arm A: Combination of lenvatinib (QD) + ifosfamide + etoposide (Days 1-3 of Cycles 1-5 only) [based on BSA calculations at Day 1 of each Cycle]; after Cycle 5 subjects will receive lenvatinib alone. Arm B: Ifosfamide + etoposide (Days 1-3 of Cycles 1-5 only) [based on BSA calculations at Day 1 of each Cycle]																		

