- p. Subjects randomized to Arm A will continue to receive lenvatinib only after completion of 5 cycles with lenvatinib+ifosfamide+etoposide until progressive disease, unacceptable toxicity, subject request, study termination by the sponsor, subject noncompliance with safety or efficacy assessments, or withdrawal of consent. Subjects randomized to Arm B will be off-treatment after 5 cycles of ifosfamide+etoposide.
- q. All subjects who receive suspension formulation, with the exception of subjects using a nasogastric or gastrostomy tube, must complete the Palatability Questionnaire according to the Schedule of Assessments. If the subject is unable to complete the questionnaire this must be done by their parents or their legal guardian.
- r. **Screening:** Tumor assessments of the chest, abdomen, pelvis, and other areas of known disease or newly suspected disease should be performed within 28 days prior to C1D1. Scans of the abdomen, pelvis, and other areas of the body may be done with MRI instead of CT, but evaluation of the chest should be done with CT. CT scans should be performed with oral and iodinated IV contrast and MRI scans should be performed with IV gadolinium chelate.

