#### 8.1.2 Randomization Phase

The Randomization Phase will consist of 2 periods: Treatment Period and Follow-up Period. The Randomization Phase will begin at the time of randomization of the first subject and will end on the data cutoff date for the PFS-1y and OS-1y analysis. Data cutoff for PFS-1y and OS-1y analysis will occur when the last subject has completed 18 cycles of treatment or discontinues before the end of Cycle 18, whichever occurs first.

After the data cutoff date for the PFS-1y and OS-1y analysis has occurred, all subjects who are still on study treatment will enter the Extension Phase.

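### The cutoff for all analyses is set by treatment cycles of the last subject, so it does not secure the one year of follow-up that PFS-1y and OS-1y need

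*Protocol*

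**What the plan says.** Section 8.7.1.6 states: "All the statistical analysis will be conducted at the PFS-1y/OS-1y analysis data cutoff date". It names the PFS-4m analysis as included and defines the date as "when the last subject has completed 18 cycles of treatment or discontinues before the end of Cycle 18, whichever occurs first". The synopsis and section 8.1.2 carry the same trigger, and section 8.1.2 adds that the Randomization Phase "will end on the data cutoff date for the PFS-1y and OS-1y analysis".

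On treatment length, Table 5 says "All cycles are 21 days in duration" and, in its study-treatment footnote, "Subjects randomized to Arm B will be off-treatment after 5 cycles of ifosfamide+etoposide". Section 8.4.1 adds: "Treatment cycles will be counted continuously regardless of dose interruptions".

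On what follows the cutoff, section 8.5.1.2.1 says: "After data cutoff for PFS-1y and OS-1y analysis, tumor assessments may be performed as clinically indicated". Table 6 (tumor-assessment footnote) adds that scans need no longer go to the imaging core laboratory. For survival, section 8.7.1.6 continues: "Additional follow-up analysis will be based on the date of data cutoff for the additional follow-up analysis for OS". No section sets a minimum calendar follow-up after the last randomization.

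**The concern.** The cutoff is named for two one-year endpoints measured from randomization, but it is triggered by time on treatment. The two coincide only for a subject who stays on lenvatinib for 18 cycles. An Arm B subject cannot do so, and an Arm A subject who progresses or stops for toxicity does not. The wording also leaves two things open:

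- whether the last subject is the last one randomized or the last one still on treatment;
- whether finishing the planned 5 cycles in Arm B counts as discontinuing.

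At stake is follow-up for PFS-1y by independent imaging review (IIR), a listed secondary endpoint. Central reading is no longer required after the cutoff, so IIR data not collected by then cannot be recovered. OS-1y at the first readout is also affected. Under the last-randomized reading, the analysis date of an open-label trial would depend on the arm and outcome of one subject.

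**Working it through.** **Inputs from the protocol.** 72 subjects randomized 1:1 (8.4.3, 8.7.2); 21-day cycles and at most 5 cycles in Arm B (Table 5); PFS-4m of 55% in Arm A and 25% in Arm B (8.7.2); study period about 36 months (synopsis).

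**Assumptions.** The protocol gives no accrual length. I take 36 − 12.4 = 23.6 months, uniform, and vary it. PFS times are exponential, matched to the two 4-month rates.

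**1. What the rule aims at.** 18 × 21 = 378 days = 54 weeks = 12.4 months. This agrees with the Week 54 scan in the assessment schedule.

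**2. What it gives when the last subject is in Arm B.** 5 × 21 = 105 days = 15 weeks = 3.45 months. The last chemotherapy day, Cycle 5 Day 3, is day 4 × 21 + 3 = 87, or 12.4 weeks. Four months is 121.75 days, or 17.4 weeks. Barring chemotherapy delays, Arm B treatment therefore ends before the 4-month landmark and well before one year. With 1:1 allocation, the last randomized subject is in Arm B about half the time.

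**3. Hand check of the one-year shortfall.** Accrual rate 72 / 23.6 = 3.05 subjects per month. With a cutoff 15 weeks after the last randomization, 3.05 × (12 − 3.45) ≈ 26 subjects have under 12 months of potential follow-up.

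**4. Simulation of both readings** (5000 trials, 23.6 months of accrual; treatment ends at progression, or at 5 cycles in Arm B and 18 in Arm A):

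| | Last randomized | Last on treatment |
|---|---|---|
| Median gap from last randomization to cutoff | 13 weeks | 45 weeks |
| Trials with gap under 12 months | about 92% | about 82% |
| Trials with gap under 4 months | about 73% | about 1% |
| Subjects with under 12 months of potential follow-up | about 26 | about 7 |
| Of these, censored event-free for PFS before 12 months | about 7 | about 0.2 |

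Under the last-randomized reading, the count with under 12 months runs from about 21 (30 months of accrual) to about 50 (12 months).

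**5. Precision of the PFS-1y difference.** A second simulation used 18, 24 and 30 months of accrual and 2% per month discontinuation for other reasons, and compared the rule with a 54-week calendar cutoff. For the last-randomized reading the ratios of mean standard errors are:

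- 0.0755 / 0.0634 = 1.19 (18 months)
- 0.0725 / 0.0638 = 1.14 (24 months)
- 0.0703 / 0.0635 = 1.11 (30 months)

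The increase is therefore 11% to 19%. For the last-on-treatment reading it is under 2% (for example 0.0647 / 0.0638 = 1.01).

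**6. Primary test.** In the same simulation, power for PFS-4m is 0.90 to 0.92 under the last-randomized reading and 0.91 to 0.92 under the calendar cutoff.

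**The case against.** **The intent is clear.** Eighteen cycles equal the Week 54 scan, and the protocol uses cycle numbers as time labels past Arm B treatment (HRQoL at C18D1). The trigger does not say last randomized, and the text after it in section 8.1.2 concerns subjects still on treatment, which suits the milder reading. This supports treating the matter as a repair of wording. It does not rescue the rule. Continuous cycle counting is stated for dose interruptions, not for the time after Arm B ends treatment, and even the milder reading usually falls short of 12 months.

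**Ending planned treatment is not discontinuing.** Table 5 says off-treatment, and section 8.5.5 describes discontinuation as stopping early. That reading is fair, but a last subject in Arm B then never fires the trigger.

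**The PFS loss is modest.** With these rates and exponential times, 1-year PFS is 0.55³ ≈ 17% and 0.25³ ≈ 2%, so most events occur early and few event-free subjects are cut off. This stands, and it is why the severity is moderate.

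A reader might infer three stronger claims that the documents do not support:

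- *The primary endpoint is compromised.* Under the last-randomized reading, about 5 subjects have under 4 months of potential follow-up and about 3 of them are censored event-free. The Kaplan-Meier analysis with Greenwood errors accommodates such administrative censoring, and power hardly moves. Under the other reading the effect disappears. Subjects censored before 18 weeks do drop out of the binomial sensitivity analysis.
- *OS-1y is permanently truncated.* Section 8.7.1.6 plans a later OS analysis, and section 8.1.3.2 continues survival follow-up every 12 weeks, until death or 2 years after end of treatment.
- *Scans stop when Arm B treatment stops.* Section 8.1.2.2 and Table 5 already require scheduled scans for subjects off treatment without progression, until progression or new anticancer therapy.

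**Conclusion.** The point holds. The rule does not guarantee one year of follow-up and is undefined on one plausible reading of its own words.

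If the last subject is the last one randomized, about 26 of 72 subjects have under 12 months of potential follow-up, about 7 are censored event-free for PFS before 12 months, and the standard error of the PFS-1y difference rises by about 11% to 19%. If it is the last subject on treatment, the cutoff still usually precedes 12 months but the PFS loss is negligible. About 7 subjects then fall short of a year of potential follow-up, which for OS affects only the first readout.

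The lasting harm is to PFS-1y by IIR. The effect on PFS-4m is small and confined to the last-randomized reading. The sizes rest on the assumed accrual and exponential times; that 5 cycles span 15 weeks and not a year rests on the protocol alone. This should be fixed, but it does not threaten the primary conclusion.

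**What to change.** In the synopsis, section 8.1.2 and section 8.7.1.6, replace the trigger with a calendar rule, for example: data cutoff is 55 weeks after the last subject is randomized (the end of the Week 54 ± 1 week scan window), irrespective of treatment status. Every subject then has at least 12 months of potential follow-up, and the cutoff no longer depends on one subject's arm or outcome. The existing scan schedule and central review simply run to that date, so nothing else in the assessments needs to change.

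The cost is a wording amendment and a readout later than the literal trigger could allow. Compared with the 54 weeks that 18 cycles imply, it is about 1 week later.

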#### 8.7.1.6.1 PRIMARY EFFICACY ANALYSIS

The primary analysis of PFS-4m rate will be based upon data provided by IIR of tumor assessments. PFS-4m rate and their Greenwood standard errors will be evaluated using the K-M estimates from both treatment groups. The statistical significance of the difference in the 2 K-M PFS-4m rates comparing lenvatinib + chemotherapy agent (Test Arm) vs. chemotherapy agent alone (Control Arm) will be tested using a 2-sided 80% CI. This 2-sided

80% CI and a p-value will be constructed using the difference of these 2 K-M PFS-4m rates and the 2 corresponding Greenwood standard errors. Statistical significance of the difference is declared if the CI is entirely above 0. This is equivalent to a test using a 1-sided test at alpha=0.1. The 2-sided 95% CIs will also be provided for descriptive purposes. PFS-4m rate will also be analyzed using a binomial approach as a sensitivity analysis by excluding subjects whose PFS are censored prior to 18 weeks.

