#### 8.4.3 Method of Assigning Subjects to Treatment Groups

This is an open-label study. All subjects who provide signed informed consent and/or assent to participate in this study and satisfy all eligibility requirements (see [Section 8.3](#)) will be assigned to treatments based on a computer-generated randomization scheme that will be reviewed and approved by an independent statistician. The randomization scheme and identification for each subject will be included in the final clinical study report for this study.

After the Baseline Period, subjects will be randomized to 1 of the following 2 treatment arms in a 1:1 ratio:

- Arm A: lenvatinib 14 mg/m^2 (orally, once daily) plus ifosfamide 3000 mg/m^2/day (IV, Day 1 to Day 3 of each cycle for a total of up to 5 cycles) and etoposide 100 mg/m^2/day (IV, Day 1 to Day 3 of each cycle for a total of up to 5 cycles)
- Arm B: ifosfamide 3000 mg/m^2/day (IV, Day 1 to Day 3 of each cycle for a total of up to 5 cycles) and etoposide 100 mg/m^2/day (IV, Day 1 to Day 3 of each cycle for a total of up to 5 cycles)

Randomization will be performed centrally by an IVRS. Randomization will follow a predefined randomization scheme based on the following stratification factors: time to first relapse/refractory disease (early [ $<18$  months] or late [ $\geq 18$  months]) and age ( $<18$  and  $\geq 18$  years). Time to first relapse/refractory disease will be calculated starting from date of initial diagnosis.

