#### 8.7.1.6.2 SECONDARY EFFICACY ANALYSES

PFS-1y rate will be analyzed using the same methods as the primary efficacy analysis. PFS censoring rules will follow FDA guidance of 2007, however, removal of baseline lesions after completion of Week 18 without progression is not a trigger for PFS censoring after 18 weeks. (refer to [Section 8.4.7.3](#) for allowed concomitant treatments/procedure in the study).

Overall survival (OS) will be compared between treatment arm and control arm using the stratified logrank test with time to first relapse/refractory disease (early [ $<18$  months] or late [ $\geq 18$  months]) and age ( $<18$  or  $\geq 18$  years) as strata. Median OS with 2-sided 80% and 95% CIs will be calculated using K-M product-limit estimates for each treatment arm, and the K-M estimates of OS will be plotted over time. The Cox regression model will be used to estimate the hazard ratio and its 80% and 95% CIs stratified by time to first relapse/refractory disease (early [ $<18$  months] or late [ $\geq 18$  months]) and age ( $<18$  or  $\geq 18$  years). Kaplan-Meier (K-M) estimates will also be presented for 4, 6, 9 and 12 months with 2-sided 80% and 95% CIs.

Overall PFS will be analyzed similarly to OS. Median PFS and 2-sided 80% and 95% (as exploratory) CIs will be presented, and the K-M estimates of PFS will be plotted over time. The Cox regression model will be used to estimate the hazard ratio and its 80% and 95% CIs stratified by time to first relapse/refractory disease (early [ $<18$  months] or late [ $\geq 18$  months]) and age ( $<18$  or  $\geq 18$  years). K-M estimates will also be presented for 4, 6, 9, and 12 months with 2-sided 80% and 95% CIs.

The ORR will be compared between the test and control groups using either a chi-square test or a Cochran-Mantel-Haenszel test stratified by time to first relapse/refractory disease (early [ $<18$  months] or late [ $\geq 18$  months]) and age ( $<18$  or  $\geq 18$  years), as appropriate. Corresponding odds ratios and their 2-sided 80% and 95% CIs comparing the groups will also be presented. The individual treatment group ORRs will also be calculated along with exact 95% confidence intervals using the Clopper and Pearson method.

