### **8.7.2 Determination of Sample Size**

A binomial-based comparison of 2 proportions using correction for continuity was used for sample size estimation. A total sample size of 72 subjects is estimated to achieve 80% statistical power at 1-sided alpha of 0.1 to detect a difference of 30% based on the assumption that PFS-4m for Arm A (lenvatinib arm) is 55% and for Arm B is 25%. Alpha is the type 1 error probability of declaring lenvatinib arm being effective when the true lenvatinib arm PFS-4m rate is only 25%.

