The management of osteosarcoma is multimodal; patients not amenable to surgery or patients at second or third relapse have a poor prognosis. Metastatic osteosarcoma is common (10% to 20%) (NCCN, Bone cancer guidelines, 2020, Casali, et al., 2018), with the most frequent site being the lung (>85%). In the case of isolated lung metastases, more than a third of patients with a second surgical remission survive for >5 years (Casali, et al., 2018). Approximately 25% of all patients with primary metastatic osteosarcoma and >40% of those who achieve a complete surgical remission may become long-term survivors (Casali, et al., 2018) as compared with 65% to 70% of patients with localized disease (Meazza and Scanagatta, 2016).

About 30% to 40% of patients with localized disease and 80% of those with metastatic disease experience relapse (Casali, et al., 2018; NCCN, Bone cancer guidelines, 2020; Ferrari, 2003). The presence of solitary metastasis, time to first relapse, and complete resectability of disease at first recurrence are the most significant prognostic indicators for improved survival. Patients whose tumor is not amenable to surgery, or with second or third recurrence, or who have metastases to the bone, have a poor prognosis. In general, despite second-line treatment, the prognosis of recurrent disease in osteosarcoma has remained poor, with long-term postrelapse survival of <20% (Casali, et al., 2018; NCCN Bone Cancer Guidelines, 2020).

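### The primary PFS-4m comparison, and PFS-1y with it, omits both randomization factors that the OS and overall PFS comparisons use: a small efficiency loss if those factors are strongly prognostic

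*Protocol*

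**What the plan says.** Protocol 8.4.3: "Randomization will follow a predefined randomization scheme based on the following stratification factors: time to first relapse/refractory disease", cut at 18 months, and age, cut at 18 years. The design section and synopsis add that the 1:1 allocation is made within the strata.

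Protocol 8.7.1.6.1 (also the synopsis, Primary Analysis): "PFS-4m rate and their Greenwood standard errors will be evaluated using the K-M estimates from both treatment groups". The 80% interval and p-value are built "using the difference of these 2 K-M PFS-4m rates and the 2 corresponding Greenwood standard errors", and superiority is declared if the interval lies above 0. The section adds: "This is equivalent to a test using a 1-sided test at alpha=0.1". No stratification factor enters.

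Protocol 8.7.1.6.2 treats the other endpoints as follows:
- PFS-1y follows the primary method.
- OS has a stratified log-rank test and a stratified Cox model with both factors. Overall PFS is analysed in the same way.
- ORR is compared "using either a chi-square test or a Cochran-Mantel-Haenszel test"; the second option is stratified by both factors, and no rule is given for choosing.

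Section 8.7.1.6.3 names no strata for the DCR and CBR differences.

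Section 6.1 says that the presence of a solitary metastasis, "time to first relapse, and complete resectability of disease at first recurrence are the most significant prognostic indicators for improved survival". It gives no PFS-4m rate by relapse timing and does not name age.

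**The concern.** The sponsor judged two factors important enough to stratify on, and uses them in the hazard-based analysis of the same PFS data. They are left out of the one comparison that decides the trial. Allocation within strata removes between-stratum variation from the true variance of the difference in rates, whereas a Greenwood standard error pooled over strata still contains it. If the strata are prognostic for 4-month PFS, the 80% interval is wider than it needs to be and some power is given away. The protocol fixes the estimator and its standard error itself, so this is not a detail left to the SAP.

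**Working it through.** **Inputs from the protocol.** 36 per arm; one-sided alpha 0.10; assumed PFS-4m 55% versus 25% (8.7.2); two binary strata (8.4.3).

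**Inputs assumed.** Stratum spreads in PFS-4m, four equal cells, blocks of 4, and no censoring before 4 months. Spreads are written relapse/age in percentage points.

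**1. The plan's own figure.** Section 8.7.2 says: "A total sample size of 72 subjects is estimated to achieve 80% statistical power at 1-sided alpha of 0.1".
- Uncorrected: m = (1.2816·√(2·0.40·0.60) + 0.8416·√(0.2475 + 0.1875))² / 0.30² = (0.8879 + 0.5551)² / 0.09 = 23.1 per arm.
- Continuity corrected: (m/4)·(1 + √(1 + 4/(0.30m)))² = 29.4, so 30 per arm and 60 in total.
- The stated inputs therefore do not give 72. With 36 per arm the corrected power is Φ((0.30 − 1/36 − 1.2816·0.1155)/0.1099) = Φ(1.130) = 87%.

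This is a separate matter; here it shows that the design has slack.

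**2. The planned test without stratum effects.** SE = √(0.435/36) = 0.110 at 55% versus 25%, and √(0.375/36) = 0.102 at 25% in both arms. Exact enumeration of the unpooled Wald test gives a one-sided error of 10.5% at a common 25% and power of 91.1% at the design effect. It is not conservative here.

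**3. Variance that the crude SE retains.** With spreads a and b in equal cells, the between-cell variance is V = a²/4 + b²/4. Under the null at 25% the large-sample ratio of crude to stratified SE is √(0.1875/(0.1875 − V)). The plug-in variance p(1 − p)/n averages (n − 1)/n of its target, so multiplying by √(35/36) = 0.986 predicts the ratio of the crude mean SE to an HC2 mean SE. Simulated ratios are crude over adjusted mean SE.

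| Spread | V | Large-sample ratio | × 0.986 | Simulated mean SEs and ratio |
|---|---|---|---|---|
| 0/0 | 0 | 1.000 | 0.986 | 0.1004 / 0.1018 = 0.986 |
| 10/5 | 0.0031 | 1.008 | 0.994 | 0.1005 / 0.1011 = 0.994 |
| 20/5 | 0.0106 | 1.030 | 1.015 | 0.100 / 0.0989 = 1.011 |
| 30/5 | 0.0231 | 1.068 | 1.053 | 0.1005 / 0.0955 = 1.052 |
| 35/10 | 0.0331 | 1.102 | 1.087 | 0.1006 / 0.0926 = 1.086 |

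So the crude SE is about 1–9% larger for relapse spreads of 20 to 35 points. For weak strata the adjusted SE is the wider one, by about 1%. At 30/5 the crude mean SE of 0.1005 compares with a true standard deviation of 0.0956.

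**4. Error and power.** Adjustment is an identity-link regression on arm and the two factors with HC2 variance. Without censoring this is what pseudo-observation regression reduces to. Values are crude / adjusted, 20,000 replicates.

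| Spread | One-sided error | Power, 20-point effect | Power, 30-point effect |
|---|---|---|---|
| 0/0 | .101 / .101 | .690 / .691 | .913 / .914 |
| 10/5 | .102 / .104 | .700 / .703 | .913 / .915 |
| 20/5 | .096 / .103 | .697 / .710 | .919 / .925 |
| 30/5 | .087 / .103 | .708 / .736 | .927 / .940 |
| 35/10 | .084 / .105 | .707 / .750 | .930 / .948 |

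Monte Carlo error on the error rates is √(0.1·0.9/20,000) = 0.2 points. Repeat runs gave a crude error of 9.3–10.0% at 20/5 and 8.2–8.5% at 35/10.

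**5. Which adjustment.** A stratum-weighted rate difference with within-cell Greenwood errors (about 9 subjects per arm per cell) rejects about 11–12% of the time under the null. A CMH-type test holds 9.5–10.2%. The regression stays near 10%.

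**The case against.** The strongest reply is that the plan is coherent as it stands. Factors enter the log-rank and Cox analyses, landmark rates are compared crudely, and the sample size in 8.7.2 is likewise an unstratified two-proportion calculation. The crude K-M difference is transparent and prespecified. The obvious stratified alternative inflates error at this sample size. Any miscalibration from prognostic strata runs toward fewer false positives, and power at the design effect is about 91–93% either way. An adjusted sensitivity analysis is ordinary SAP content, and the SAP is not at hand.

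Most of this stands, and it sets the severity. It does not remove the point. The protocol makes the crude comparison the decision rule, and a well-behaved adjusted estimate of the same rate difference exists at no cost in data or, in any scenario run, in power.

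A reader might also infer that chance imbalance in relapse timing is left in the estimate. Allocation within strata on that very factor leaves only residual imbalance from incomplete blocks; the issue is the standard error.

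**Conclusion.** The omission is real and small. For assumed relapse-time spreads of about 20 to 35 points, the Greenwood SE is about 1–9% too large and the one-sided error is about 8–10%. Adjustment would gain about 1–4 power points at a 20-point effect and 1–2 points at 30. With weaker strata there is no power to gain and none to lose, and the adjusted SE is on average about 1% wider. These sizes rest on assumed spreads, equal cells, small blocks and no early censoring. They were worked out for PFS-4m only; for PFS-1y the same reasoning gives the direction but not a size.

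Three stronger readings are not supported:
- **That the strata are used everywhere except in the primary test.** PFS-1y and the DCR and CBR differences are also unstratified, and ORR may be.
- **That the primary test is conservative as a matter of fact.** Without stratum effects its exact error is 10.5%. Section 6.1 speaks of survival, not 4-month PFS, and gives no rates.
- **That validity or the stated power is in danger.** The error does not exceed about 10.5%, and the power of the planned test is above 80% at the design effect.

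This is a minor improvement in efficiency and internal consistency.

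**What to change.** In 8.7.1.6.1, the PFS-1y sentence of 8.7.1.6.2 and the synopsis:
- Estimate the difference in PFS rates by identity-link regression on K-M pseudo-observations at the landmark, with arm and the two randomization factors as randomized, and HC2 variance. The target remains the difference in K-M rates.
- Report the same 80% and 95% intervals, and keep the decision rule.
- Keep the crude K-M difference with Greenwood errors as the supportive analysis.
- Do not use a stratum-weighted K-M difference with Greenwood variance.
- Fix the ORR comparison as the stratified CMH test, which removes the open choice.

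If the sponsor prefers the crude difference as primary, the adjusted analysis should at least be a prespecified sensitivity analysis. The cost is a wording change and one regression, with no new data and no change in sample size.
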